**Definition of Final Treatment Visit Value**

The Final Treatment Visit value is defined as the last non-missing measurement collected after Study Day 1 and on or before Study Drug End Day 2.

**Final Post-Treatment Value**

The final post-treatment value for each subject is the last non-missing measurement collected after Study Drug End Day 2.

## 6.2 Definition of Analysis Windows

The time windows specified in [Table 1](#) for Substudy 1, [Table 2](#) for Substudy 2 and [Table 3](#) for Substudy 3 describe how data are assigned to protocol specified time points. Time windows specified in [Tables 1 and 2](#) will also be used for resistance analyses. However, for resistance analyses, the windows relative to the end of DAA dosing ([Table 2](#)) will be irrespective of the end of pegIFN/RBV dosing.

The subject will continue to be monitored for antiviral drug resistance for 48 weeks following the last dose of study drug. If the subject discontinues DAA study drug/Substudy 1 and continues to receive pegIFN/RBV, the subject will follow the PR Treatment visit schedule, as specified in [Table 2](#), and then subsequently follow the Post-Treatment visit schedule, as specified in [Table 3](#), following the last dose of pegIFN/RBV. However, if the subject discontinues DAA study drug and pegIFN/RBV, the subject will follow the Post-Treatment visit schedule for 48 weeks following the last dose of study drug, specified in [Table 3](#).

If more than one assessment is included in a time window, the assessment closest to the nominal time should be used. If there were two observations equal distant to the nominal time the latest one will be used in analyses. The only exception to this is for the SVR windows; for these windows, the last value in the window will be used.

If multiple measurements are made on the same day for a safety laboratory parameter or a vital sign parameter, the average of the values will be used in analyses. For summaries of shifts from baseline and potentially significant values, multiple values on the same day will not be averaged; all values will be considered for these analyses.

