### **11.3 Analysis of Laboratory Data**

Data collected from the local laboratory as a result of additional testing due to an SAE will be used in analyses in addition to the data collected from the central laboratory.

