### 11.3.2 Statistical Methods

Mean changes from baseline to each post-baseline visit, including applicable post-treatment visits, will be summarized for each protocol-specified laboratory parameter, including IP-10, with the baseline mean, visit mean, change from baseline mean, standard deviation, and median.

Laboratory data values, excluding IP-10, will be categorized as low, normal, or high based on normal ranges of the laboratory used in this study. Shift tables from baseline to minimum value (related to the normal range), maximum value (related to the normal range) and final values during DAA treatment (DAA Study Drug End Day  $\leq 2$ ) will be created. The shift tables cross tabulate the frequency of subjects with baseline values below/within/above the normal range versus minimum/maximum/final values below/within/above the normal range. The shift tables will also cross tabulate the frequency and percentage of subjects with baseline values below/within the normal range versus minimum/maximum/final values below/within/above the normal range. The shift tables will also cross tabulate the frequency and percentage of subjects with baseline values within/above the normal range versus minimum/maximum/final values below/within/above the normal range.

Frequencies and percentages of subjects with post-baseline chemistry and hematology values during DAA treatment (DAA Study Drug End Day  $\leq$  2) meeting criteria for Potentially Clinically Significant (PCS) Laboratory Values (Table 5 and Table 6) will be summarized. A post-baseline value must be more extreme than the baseline value to be considered as a PCS finding. Listings will be provided that presents all of the subjects and values meeting the PCS criteria (at any time during the study).

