For the liver function tests of ALT and AST, the frequency and percentage of subjects with a maximum CTCAE Grade of 1, 2, 3, or 4 (see definitions in Table 8) at any post-nadir visit (regardless of the baseline value) through the end of DAA treatment (DAA Study Drug End Day  $\leq$  2) will be summarized. For hemoglobin, creatinine clearance, alkaline phosphatase, and total bilirubin, the frequency and percentage of subjects with a maximum CTCAE Grade of 1, 2, 3, or 4 (see definitions in Table 7) at any post-baseline visit (regardless of the baseline value) through the end of DAA treatment (DAA Study Drug End Day  $\leq$  2) will be summarized. The summaries will include rows for the number and percentage of subjects with at least Grade 2 and at least Grade 3 laboratory abnormalities. Accompanying listings of all ALT, AST, total, indirect and direct bilirubin, and alkaline phosphatase (as available) will be created for any subject who had at least a Grade 3 ALT, AST, alkaline phosphatase, or total bilirubin. A similar listing will be provided for hemoglobin that includes all hemoglobin, total neutrophils, platelet count, and WBC values and for creatinine clearance that includes creatinine clearance, eGFR and creatinine values.

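### SAP 6.2 does not clearly exempt the maximum-CTCAE-grade and ALT/bilirubin summaries from same-day averaging, so a duplicate sample can lower a worst-value result

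*SAP*

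**What the plan says.** SAP 6.2 sets the default for several same-day results on one safety laboratory or vital sign parameter: "the average of the values will be used in analyses". It then gives one exception: "For summaries of shifts from baseline and potentially significant values, multiple values on the same day will not be averaged", and for those summaries every value counts.

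SAP 11.3.2 describes four outputs of different kinds:

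- shift tables against the normal range;
- PCS tables and listings, using the limits in SAP Tables 5 and 6;
- tables of subjects "with a maximum CTCAE Grade of 1, 2, 3, or 4", using SAP Table 7, with listings for subjects who reach Grade 3;
- counts of subjects meeting combined ALT and total bilirubin criteria, with a listing for the ALT ≥ 3 × ULN and bilirubin ≥ 2 × ULN group.

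The last two carry no same-day rule of their own.

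SAP 11.3 adds a possible source of duplicates: "Data collected from the local laboratory as a result of additional testing due to an SAE will be used in analyses in addition to" the central-laboratory data. No rule says how a local and a central result from the same day are combined.

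**The concern.** The exception shows that the authors saw averaging as unsuitable where the aim is to find an extreme value. Maximum-grade tables and ALT/bilirubin counts have the same aim, yet the wording does not name them, so a programmer following the text would average first and grade afterwards.

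An averaged result is never more extreme than the worse of the two values it replaces. Any error in a maximum grade is therefore an under-count. Two tables in the same report could also disagree about one subject at the same numerical limit, and a subject averaged below Grade 3 may drop out of the listing that is triggered by Grade 3.

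**Working it through.** The plan states no figure to reproduce. The check applies the plan's own limits to same-day pairs, once averaged and once with all values considered. **All pairs are assumed for illustration.**

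**Inputs.** Grade 3 limits are from SAP Table 7, PCS limits from SAP Tables 5 and 6, the ALT/bilirubin criterion from SAP 11.3.2, and the cap of 35 subjects from the protocol synopsis.

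**Step 1: effect of averaging.** For a pair (a, b) the averaged value is (a + b)/2.

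| Parameter | Pair | Mean | Result averaged | Result, all values |
|---|---|---|---|---|
| ALT (× ULN) | 5.6, 4.2 | 9.8/2 = 4.9 | Grade 2 | Grade 3 |
| Total bilirubin (× ULN) | 3.4, 2.4 | 5.8/2 = 2.9 | Grade 2 | Grade 3 |
| Haemoglobin (g/L) | 78, 84 | 162/2 = 81 | Grade 2 | Grade 3 |
| ALT with bilirubin (× ULN) | 3.3, 2.5 with 2.2, 1.6 | 2.9 with 1.9 | criterion missed | criterion met |

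For ALT and AST the grade is taken after the nadir, so the direction holds for a given nadir. The second ALT/bilirubin count (ALT > 5 × ULN with bilirubin < 2 × ULN) has an upper bilirubin limit, so averaging can also move a subject into it. With ALT 5.6 × ULN and bilirubin 2.2 and 1.6 × ULN, the mean bilirubin of 1.9 puts the subject there instead of in the first count.

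**Step 2: what the unaveraged PCS tables still catch.** A PCS value must also be more extreme than baseline.

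| Parameter | PCS limit | Grade 3 starts at | Grade 3 values covered by PCS? |
|---|---|---|---|
| Haemoglobin | < 80 g/L | < 80 g/L | yes, same limit |
| Total bilirubin | ≥ 2 × ULN | > 3 × ULN | yes |
| Alkaline phosphatase | > 1.5 × ULN | > 5 × ULN | yes |
| Creatinine clearance | < 50 mL/min | < 29 mL/min | yes |
| ALT, AST | > 5 × ULN and ≥ 2 × baseline | > 5 × ULN | only in part |

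For haemoglobin 78 and 84 g/L, the PCS table counts the subject (78 < 80) while the averaged grade table shows Grade 2 (81). The event is not lost, but the tables disagree.

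**Step 3: the ALT/AST gap.** With baseline b (× ULN), PCS requires a value above 5 and at least 2b. The second condition is the stricter one when 2b > 5, that is b > 2.5. Protocol 5.2.2 excludes only screening ALT or AST above 7 × ULN, so such baselines can occur. With b = 3, PCS needs at least 6. The pair 5.6 and 4.2 is then not PCS, and averaged to 4.9 it is not Grade 3 either.

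**Step 4: the ALT/bilirubin gap.** ALT between 3 and 5 × ULN has no PCS counterpart. The bilirubin value can appear under PCS, but no other table reports the combination. Its listing is triggered by the same criterion and would miss the same subject.

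**Step 5: weight of one subject.** 1/35 = 2.9%. The Wilson 95% interval is 0.0 to 9.9% for 0/35 and 0.5 to 14.5% for 1/35. In the protocol's Table 3, ALT > 5 × ULN occurred in 0 to 2.9% of subjects on active arms. If similar rates applied here, although the regimen differs, 35 × 0.029 = 1.0, so about 0 to 1 subject is expected and one averaged-down case could be the whole count.

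**The case against.** **Same-day repeats.** A reader might infer from the confirmatory tests in protocol 6.7.2 to 6.7.4 that same-day duplicates are built into the trial. The text does not support that. Those sections ask for repeat or confirmatory tests without placing them on the same day, and the follow-up liver chemistry in 6.7.4 is due within a week. Samples go to a central laboratory, so a repeat prompted by a result would ordinarily come later, and a later-day repeat is not averaged under this rule. SAP 11.3 does not say that local samples taken for an SAE share a day with central ones. This objection stands: the mechanism is possible, and its frequency is unknown.

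**A broader reading of the exception.** SAP 6.2 speaks of potentially significant values, not of the defined PCS term used in SAP 11.3.2. A programmer could take it to include Grade 3 and 4 results. That is fair, but the text then allows two readings that give different tables, which is a reason to settle the wording.

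**Capture elsewhere.** It would be tempting to say that Grade 3 events disappear from the report. For haemoglobin, bilirubin, alkaline phosphatase and creatinine clearance they mostly do not, because the PCS tables and listings use every value. This stands, and leaves the gaps in steps 3 and 4.

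**Local values and visit means.** A reader might also conclude that local values distort the by-visit means. SAP 6.2 selects by proximity ("the assessment closest to the nominal time should be used"), so a local result enters a visit mean only if it is the one selected or falls on the same day as the selected one. Nor does the plan say that local results are judged on central limits. Restricting means to central values is a preference, not the correction of an error.

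**Conclusion.** The point holds as a gap in wording with a known direction. On the literal text, two worst-value outputs fall under an averaging rule that can lower a maximum grade, or miss an ALT ≥ 3 × ULN with bilirubin ≥ 2 × ULN case, and that can set the grade table against the PCS table at the shared haemoglobin limit of 80 g/L.

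The size is probably small. Each affected subject is 2.9 percentage points if 35 are enrolled. That is the weight of one case and not an expected effect, because the documents do not say how often same-day duplicates occur. The events that could go unreported in every table are narrower: ALT or AST just above 5 × ULN in subjects with a baseline above 2.5 × ULN, and the ALT/bilirubin combination.

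The conclusion assumes that the exception is read literally and that same-day discordant pairs occur at least occasionally. The tables are descriptive, and no efficacy result is affected.

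**What to change.** In SAP 6.2, extend the no-averaging, all-values rule to the maximum-CTCAE-grade summaries, the ALT/bilirubin criteria and the listings attached to both. The same sentence should say whether the ALT and AST nadir is also found from all values.

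The cost is one SAP sentence and a matching line in the table programs. It needs no new data and no protocol amendment. Limiting by-visit means to central-laboratory values is optional.

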**Table 1. DAA + PR Treatment (TI Period, Substudy 1) Visit Windows**

Scheduled Time	Nominal Day (Study Day)	Time Window (Study Days Range)
Baseline	1	$\leq 1$
TI Week 1	7	2 to 10
TI Week 2	14	11 to 21
TI Week 4	28	22 to 42
TI Week 8	56	43 to 70
TI Week 12	84	71 to 98
TI Week 16	112	99 to 126
TI Week 20	140	127 to 154
TI Week 24	168	155 to 182
Final DAA Treatment Visit	Last Visit with Study Day $> 1$ and DAA Study Drug End Day $\leq 2$	

Notes: Data must also have DAA study drug end day  $\leq 2$  for all windows.  
 The result closest to the scheduled time point will be used.

**Table 2. PR Treatment (Substudy 2)/Post-DAA Visit Windows**

Scheduled Time	Nominal Study (DAA Study Drug End Day)	Time Window (DAA Study Drug End Days Range)
PR/Post-DAA Week 2	14	3 to 21
PR/Post-DAA Week 4	28	22 to 42
PR/Post-DAA Week 8	56	43 to 70
PR/Post-DAA Week 12	84	71 to 126
PR/Post-DAA Week 24	168	127 to 210
PR/Post-DAA Week 36 a	252	211 to 294
PR/Post-DAA Week 48 a	336	295 to 378
Final Treatment Visitb	Last Visit with Study Day > 1 and Study Drug End Day ≤ 2	

a. These Substudy 2 visits are only needed for subjects who did not complete 24 weeks for pegIFN/RBV in Substudy 1 such that a subject completes a total of 48 weeks of pegIFN/RBV across Substudies 1 and 2. However, the Post-DAA Week 48 window may be used for resistance analyses, regardless of the number of Substudy 2 visits.

b. Final Treatment Visit is defined for all subjects, regardless of whether the subject enters Substudy 2.

Note: For efficacy analyses of HCV RNA and safety analyses, all scheduled time points, except Final Treatment Visit, will apply only to subjects who received pegIFN/RBV in Substudy 2.

For efficacy analyses of HCV RNA and safety analyses, data must also have DAA Study Drug End Day > 2 and PR End Day ≤ 2 for all scheduled time points, except Final Treatment Visit.

For resistance analyses, data must have DAA Study Drug End Day > 2 for all scheduled time points.

Resistance data included in Post-DAA windows may have been collected either during PR Treatment or Post-Treatment.

The result closest to the scheduled timepoint will be used.

**Table 3. Post-Treatment (Substudy 3) Visit Windows**

Scheduled Time	Nominal (Study Drug End Day)	Time Window (Study Drug End Days Range)
PT Week 2	14	3 to 21
PT Week 4	28	22 to 42
PT Week 8	56	43 to 70
PT Week 12	84	71 to 126
PT Week 24	168	127 to 210
PT Week 36	252	211 to 294
PT Week 48	336	295 to 378
Final Post-Treatment Visit	Study drug end day > 2	
SVR 4	28	3 to 56
SVR 12	84	57 to 126
SVR 24	168	127 to 210

Notes: The result closest to the scheduled timepoint will be used, except for SVR endpoints. For SVR windows, the last value in the window will be used.

Blood samples for chemistry, hematology, and urinalysis are only scheduled to be collected at PT Weeks 2 and 4 during the Post-Treatment Period.

HCV RNA measurements taken after the start of another anti-viral treatment will be excluded.

### 6.3 Definition of Missing Data Imputation

Imputations for missing data will be performed when analyzing RVR, Final Treatment Visit Response, eRVR, and all SVR endpoints.

#### HCV RNA

HCV RNA values will be selected for analysis based on the analysis windows defined in Section 6.2. When there is no HCV RNA value in a defined visit window, the closest values before and after the window will be used for flanking imputation, regardless of the value chosen for the subsequent and preceding window.

For flanking imputation, if a subject has a missing HCV RNA value at a post-baseline visit but with undetectable or unquantifiable HCV RNA levels at both the preceding value and the succeeding value, then the HCV RNA level will be imputed as undetectable or

unquantifiable, respectively, at this visit for this subject. In addition, if a subject has an unquantifiable HCV RNA level at the preceding value and an undetectable HCV RNA level at the succeeding value, or vice versa, the HCV RNA level will be imputed as unquantifiable at this visit for this subject.

For analyses of SVR, subjects still missing visit values after flanking imputation will have backward imputation applied. For backward imputation, if the nearest HCV RNA value after the SVR window is unquantifiable or undetectable, then it will be used to impute the HCV RNA value in the SVR window.

For analyses of RVR, Final Treatment Visit Response, eRVR, and SVR, subjects still missing a value for the visit window associated with the analysis after performing the imputations described above will be imputed as a failure.

If a subject starts another treatment for HCV, then all HCV RNA values for this subject measured on or after the start date of the new HCV treatment will be excluded from analyses. The subject will be considered a failure for summaries of viral response at all time points after the start of the new HCV treatment.

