##### **4.1.2 Secondary Objective**

The secondary objectives of this study are:

- to evaluate the percentage of subjects with sustained virologic response 24 weeks post-dosing (SVR24; HCV RNA < LLOQ 24 weeks after the last dose of study drug) and
- to evaluate the percentage of subjects with extended rapid virologic response (eRVR) (HCV RNA < LLOQ at Weeks 4 through 12 of therapy with ABT-450/r plus ABT-267 plus pegIFN plus RBV).

[figure not shown]

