## 10.3 Secondary Efficacy Analyses

The secondary efficacy endpoints are the percentage of subjects with sustained virologic response 24 weeks after the last actual dose of study drug (including DAA, pegIFN, and RBV) (SVR24; HCV RNA < LLOQ 24 weeks after the last actual dose of study drug) and the percentage of subjects with eRVR (HCV RNA < LLOQ at TI Weeks 4 through 12).

The percentage of subjects with SVR24 and eRVR and the corresponding 95% Wilson score confidence intervals will be calculated.

A subject will be considered to have e RVR if after all missing data are imputed according to rules specified in Section 6.0, he/she has HCV RNA levels below LLOQ at TI Week 4 and TI Week 12 with no confirmed HCV RNA  $\geq$  LLOQ in between. If a subject is missing HCV RNA data at either TI Week 4 or 12 then the subject will be considered an eRVR failure.

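### Flanking imputation for RVR and eRVR can use HCV RNA samples taken after the DAAs were stopped, although the on-treatment windows exclude such samples and the objective defines eRVR on the four-drug regimen

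*SAP*

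**What the plan says.** **Objective.** SAP Section 4.1.2 (and protocol Section 4.2) defines eRVR as HCV RNA below LLOQ "at Weeks 4 through 12 of therapy with ABT-450/r plus ABT-267 plus pegIFN plus RBV".

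**Windows.** SAP Table 1 sets the TI Week 4 window at Study Days 22 to 42 and the TI Week 12 window at Study Days 71 to 98. Its note adds a condition for all its windows: "Data must also have DAA study drug end day" of at most 2. Later samples belong to the PR/Post-DAA windows of Table 2.

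**Imputation.** Section 6.3 states: "Imputations for missing data will be performed when analyzing RVR, Final Treatment Visit Response, eRVR, and all SVR endpoints". For an empty window, "the closest values before and after the window will be used for flanking imputation", and this applies "regardless of the value chosen for the subsequent and preceding window". If the preceding and succeeding values are both unquantifiable or undetectable, the missing visit is imputed as such. The only values that Section 6.3 removes are those on or after the start of another HCV treatment. Protocol Section 8.0 has the same flanking rule, also without an on-DAA condition.

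**Scoring.** Section 10.3 judges eRVR "after all missing data are imputed according to rules specified in Section 6.0": below LLOQ at TI Weeks 4 and 12, with no confirmed quantifiable value between. It closes by saying that a subject with missing Week 4 or Week 12 data is an eRVR failure.

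**The concern.** The SAP separates on-DAA from post-DAA samples when it fills a window with observed data, and drops that separation when it fills the same window by imputation. Stopping the DAAs early and continuing pegIFN/RBV in Substudy 2 is a path the protocol provides for, and pegIFN/RBV there is study drug. The exclusion for another HCV treatment therefore does not remove those samples. A subject who stops all drugs also keeps giving HCV RNA samples in Substudy 3.

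The rule fits neither possible meaning of the endpoint. If eRVR means response on the four-drug regimen, a subject who left the DAAs before the Week 12 window has not shown it. If it means response regardless of stopping the DAAs, the sample actually drawn near Day 84 should be used. The SAP sets that sample aside as off-DAA, then imputes from other off-DAA samples.

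Compared with scoring failure, the imputation can only add responders. The results exposed are the secondary endpoint eRVR, the additional endpoint RVR, and the SVR12 subgroup by achievement of eRVR in Section 10.8.

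**Working it through.** The documents give no expected eRVR rate and no expected number of early DAA stops, so there is no planned figure to reproduce. The check applies the SAP rules to day counts.

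**Inputs.** Windows and the End Day limit come from SAP Table 1. PR visits at Weeks 2, 4, 8 and 12 after the last DAA dose (DAA End Days 14, 28, 56, 84) come from SAP Table 2. Enrolment of up to 35 comes from the protocol synopsis. Assumption: the TI discontinuation visit falls on the last DAA day.

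**Step 1: when can no sample qualify?** A sample qualifies only if its study day is at most the last DAA day + 2.
- TI Week 12 opens on Day 71. Last dose Day 68: 68 + 2 = 70 < 71, so the window must be empty.
- TI Week 4 opens on Day 22. Last dose Day 19: 19 + 2 = 21 < 22, so the window must be empty.

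For a slightly later last dose, a discontinuation sample within 2 days may fall in the window. That would be an observed value, not an imputed one.

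**Step 2: which values then flank the window?**

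| Last DAA day | Window | Sample barred as off-DAA | Value before | Value after |
|---|---|---|---|---|
| 56 | TI Week 12 | Day 84 (28 days off) | Day 70 (14 days off) | Day 112 (56 days off) |
| 28 | TI Week 12 | Day 84 (56 days off) | Day 56 (28 days off) | Day 112 (84 days off) |
| 19 | TI Week 4 | Day 33 (14 days off) | Day 19 (last DAA day) | Day 47 (28 days off) |

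In the first two rows the TI Week 4 sample (Day 28) is observed on DAAs. If it and both flanking values are below LLOQ, with no confirmed quantifiable value between Weeks 4 and 12, the subject counts as eRVR. In the second row that follows only four weeks of DAAs. In every row, requiring DAA End Day of 2 or less leaves no succeeding value, so the subject stays missing and is scored a failure.

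**Step 3: effect per subject.** Each such subject changes the rate by 1/N: 1/35 = 2.9 points, or 1/20 = 5.0 points at an assumed 20 enrolled.

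Illustration, assuming 28 of 35 eRVR under the restricted rule (Wilson 95% intervals, the SAP's method):

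| Extra imputed responders (assumed) | eRVR | 95% interval |
|---|---|---|
| 0 | 80.0% | 64.1 to 90.0 |
| 1 | 82.9% | 67.3 to 91.9 |
| 2 | 85.7% | 70.6 to 93.7 |
| 3 | 88.6% | 74.0 to 95.5 |

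From an assumed 21 of 35 (60.0%; 43.6 to 74.4), one extra responder gives 62.9% (46.3 to 76.8).

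**The case against.** **The closing sentence of Section 10.3 may already solve this.** Read alone, it makes any missing Week 4 or Week 12 value an eRVR failure. However, the sentence before it scores eRVR after imputation, Section 6.3 assigns failure only to values still missing after imputation, and protocol Section 8.0 uses the same order. It does not close the gap, but it leaves the text ambiguous.

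**A reader might infer that a real quantifiable result is replaced by an imputed response.** The documents do not settle this. It requires reading the value after the window as the first one beyond the study-day range. Section 6.3 also speaks of the preceding and succeeding values. If the succeeding value is the next post-DAA sample, the barred Day 84 value is itself the flank, and a quantifiable result there blocks the imputation. In addition, a single unconfirmed quantifiable value between the Week 4 and Week 12 assessments does not fail eRVR under Section 10.1. On both readings, though, the succeeding value is off-DAA, and that is the point made here.

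**The exposed group is narrow.** This stands. Subjects who stop the DAAs under the TI Week 4 virologic criterion (protocol Section 5.4.1.1) already fail RVR and eRVR at Week 4. Several toxicity rules in protocol Section 6.7 act on all study drugs, not the DAAs alone. Both flanks must also be below LLOQ. Zero affected subjects is plausible.

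**The stakes are modest.** This also stands. The study is single-arm and descriptive, and no decision rule uses eRVR or RVR. Nor does the SAP require a full 12 weeks on DAAs: Table 1 would accept a Day 71 sample after a last dose on Day 69.

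**Conclusion.** The concern holds in this form: a stated imputation rule conflicts with the SAP's own window restriction and with the wording of its secondary objective. It lets off-DAA samples establish Week 12 or Week 4 response for suppressed subjects whose last DAA dose was on or before Day 68 or Day 19 respectively.

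The size is 2.9 percentage points per affected subject at 35 subjects, and more if fewer enrol. The count is unknown and may be zero; the range of 0 to 3 in the working is an assumption without support in the documents. The day counts assume visits on their nominal days.

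A reader might infer that the primary result is biased, or that early DAA stoppers in general are scored as responders. Neither follows. The SVR12 rate does not depend on the TI windows, and subjects who stop for non-response largely fail on their own values. What is affected is eRVR, RVR and the SVR12-by-eRVR subgroup.

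**What to change.** 1. In SAP Section 6.3, add that for RVR and eRVR both flanking values must have DAA Study Drug End Day of 2 or less, as in Table 1; otherwise the subject is a failure for that endpoint. A subject who merely missed a visit while still on DAAs can then still be imputed.
2. Leave flanking and backward imputation for the SVR windows unchanged.
3. Reword the last sentence of the eRVR rule in Section 10.3 so that failure applies to values still missing after this restricted imputation.
4. Record the departure from protocol Section 8.0 in SAP Section 12.1.1.

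If the sponsor instead intends eRVR to count regardless of stopping the DAAs, that is coherent too. The SAP should then say so, use the samples observed at those times, and align the objective.

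The cost is one programming condition and a few sentences. The downside is that eRVR and RVR may be slightly lower.
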